Before the trial	Onboarding phase	Adopt a flexible onboarding period for 'slow onboarding users' if needed - ideally a user completes screening in 2 or 3 weeks (nudged to do so), but if they don't, they enter the trial (randomisation) when they have met the baseline criteria, rather than after a predetermined window of time.	HUL
		The latest calendar date that a user can complete onboarding (pass screening) is the last day of the recruitment window.	
During the trial	Recruitment	Extend the recruitment period beyond 6 weeks if necessary	HUL
During the trial (triggered at M5)	Trial period	Make data collection attractive: Consider encouraging wearing and syncing the wearable device with the app in the crucial data collection weeks at m3 and m5 with a small payment (£10), if attrition is deemed relatively too high ¹³ at the data collection point at m1 and m3.	HUL
During the trial (triggered at M3 and M5)	Trial period	Make data collection attractive: Consider encouraging filling in Intake24 at m3 and m5 with a larger payment (£10), if attrition is	HUL

¹³ We consider the attrition too high if the number of users not providing their data 10% smaller than expected at the start of the 1 month mark (see Table 6 for the expected attrition at different trial stages).

		deemed relatively too high ¹⁴ at the data collection point at m1. At m5 - for PA, users will receive £5 for syncing their fitness tracker (any amount of data > 0) during weeks 21 and 22 - up to 2 times so they can earn up to an extra £10.	
During the trial (triggered)	Trial period	Extend the data collection window from 2 to 3 weeks (21 days) at m3 and m5 for all measures (i.e. Intake24, steps, WHO5, sleep and weight)	HUL
During the trial	Trial period	Pull data collection forward. Change M5 data collection window to start earlier i.e. during the 20th week (day 134 to day 155).	HUL
After the trial	Recruitment and baseline phase	Shift the focus of the evaluation to a shorter follow-up (e.g. after 3 months of treatment instead of 5 months). If the sample size at 5m is less than 80% of the total sample size (n = 4,200) that the trial requires in order to detect a minimum effect size for primary outcomes (see Table 7 for details), we will use data from the 3m mark instead of the 5m mark in the analysis. ¹⁵	BIT

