2.2.4 Randomisation

Randomisation will be conducted at the household level. This approach has two advantages over individual-level randomisation: (i) avoids the risk of contamination within the same household (but opens up the possibility of additive effects of multiple household members being in treatment together); (ii) reduces the risk that we alienate and / or confuse users in the control group whenever they cohabit with someone assigned to a treatment arm.

Users will enter randomisation only if/when they have completed the baseline phase. This implies that the day of randomisation is different across users even within the same households: it always happens at the end of their baseline phase (if successful), but the exact calendar day depends on when they have downloaded the app, when they have completed the onboarding, and how long it took them to complete the baseline phase (see Figure 1 for an example from a user's perspective).

The randomisation algorithm developed by HUL would then:

1. Check if another user from the same household has already been randomised

¹⁴ We consider the attrition too high if the number of users not providing their data is 10% smaller than expected at the start of the 1 month mark (see Table 6 for the expected attrition at different trial stages).

¹⁵ Results for the 5m mark will still be reported; however, we will rely on results from the 3m mark to provide an assessment of the impact of offering financial incentives.

based on their full addresses (including postcode).

- 2. If YES, the algorithm assigns this user to the same trial arm
- 3. If NO, the algorithm generates a random number from 1-100 (inclusive) for the user.
- 4. Based on the rule described in Figure 2, users are assigned to one of the 4 trial arms. Note that the control arm will be larger than the other arms. This is because at the analysis stage (5m mark), we aim at having 3 users in the control group for each user in the treatment arms. However, we expect attrition to differ across control and treatment groups, as shown in Table 6 in Section 2.4.2.4.. Based on these attrition estimates, at randomisation 12% of users will be assigned to the high incentive arm, 12% to the medium incentive arm, 15% to the low incentive arm, 61% to the control arm.

BIT's in-house IT expert will quality assure the code of the randomisation algorithm developed by HUL before the trial launch.

Figure 1. Onboarding and baseline phase from a user's point of view¹⁶.

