Number of overall users required for smaller dietary outcome target MDES at the 5m mark analysis stage	4,200 (2,100 in control; 700 per intervention arm)			

⁴⁶ The Benjamini-Hochberg false discovery adjustment will be applied during analysis of primary outcomes, but as it is not possible to apply this before having the data, the more conservative Bonferroni adjustment provides an upper bound on power here.

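### Footnotes 13 and 14 define attrition as too high when fewer users than expected fail to provide data, which reverses the trigger for the retention payments; the single 5-to-3-month switch also suits diet but not activity

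*Protocol*

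**What the plan says.** **Payment trigger.** Two rows of Table 2 (section 2.2.3) foresee extra payments for data collection. The Intake24 row reads "Consider encouraging filling in Intake24 at m3 and m5 with a larger payment (£10), if attrition is" and goes on to make this depend on attrition at month 1 being judged relatively too high. The row on wearing and syncing the device has the same form and looks at months 1 and 3. The judgement is defined only in the footnotes. Footnote 13: "We consider the attrition too high if the number of users not providing their data 10% smaller than expected". Footnote 14: "We consider the attrition too high if the number of users not providing their data is 10% smaller than expected". Both take the 1-month mark as reference and point to Table 6 for the expected attrition.

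**Switch of time point.** The last row of Table 2 begins "If the sample size at 5m is less than 80% of the total sample size (n = 4,200" and then says that 3-month data will be used in place of 5-month data. Footnote 15 qualifies this: "Results for the 5m mark will still be reported; however, we will rely on results from the 3m mark" for the assessment of impact. Section 2.6.3.7 describes the same switch differently, as applying when 5-month attrition would rule out a meaningful analysis at that time. Table 5 gives the sample size as "4,200 (2,100 in control; 700 per intervention arm") and labels it as the number needed for the smaller, dietary target effect.

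**The concern.** The footnotes reverse the intended direction. A rule meant to protect retention is satisfied when retention is better than planned and is silent when it is worse. Section 2.6 names attrition as the largest threat to the evaluation, and the footnotes are the only place where the decision to intervene is given a number.

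The switch raises a separate and smaller question. One threshold, taken from a diet calculation, governs all six primary outcomes. For the two activity outcomes it could move the basis of the conclusion away from the pre-planned 5-month comparison while that comparison still had ample power for its own target.

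**Working it through.** **1. Payment trigger (Table 6 totals).**

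- Expected at randomisation: about 15,500. Expected to provide data at 1 month: about 11,900.
- Expected non-providers: 15,500 − 11,900 = 3,600.
- As written (non-providers 10% below plan): 0.9 × 3,600 = 3,240 or fewer, so 15,500 − 3,240 = 12,260 or more providing. That is 79% retention against 77% planned.
- Reversed, counting non-providers (10% above plan): 1.1 × 3,600 = 3,960 or more, so 11,540 or fewer providing.
- Reversed, counting providers (10% below plan): 0.9 × 11,900 = 10,710 or fewer providing, so 4,790 or more non-providers.

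At 4,790 non-providers, a third more than planned (4,790 / 3,600 = 1.33), the written condition is still not met. The two possible corrections differ by 11,540 − 10,710 = 830 users, so the intended threshold cannot be recovered from the wording.

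**2. Reproducing the stated detectable effects at 4,200.** Inputs: 2,100 control against 2,100 pooled, 80% power, Bonferroni by family (2 activity, 4 diet), ICC 0.3, baseline correlation 0.5, and the SDs in Table 5. An overall two-sided alpha of 0.05 is my assumption, giving 0.025 for activity and 0.0125 for diet.

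MDES = (z₁₋α/₂ + z₀.₈) × SD × √[(2/2100) × DE × (1 − 0.5²)]

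The worked example in Appendix B treats 39/41/20% as shares of participants. That gives an effective fraction of 0.389 + 0.409/1.3 + 0.202/1.6 = 0.830, so DE = 1.205.

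| Outcome | Computed | Stated (Table 7) |
|---|---|---|
| MVPA (min/day) | 2.35 | 2.4 |
| Steps/day | 370 | 371 |
| Fruit and vegetables (g/day) | 18.6 | 18.7 |
| Fibre (g/day) | 0.735 | 0.74 |
| Free sugars (% food energy) | 0.617 | 0.63 |
| Saturated fat (% food energy) | 0.314 | 0.31 |

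All six agree within 3%.

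**3. Users needed for the Table 5 targets.**

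N = 4 × [(z₁₋α/₂ + z₀.₈)/d]² × 0.75 × DE

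- Activity, d = 0.2: 4 × (3.083/0.2)² × 0.75 × 1.205 ≈ 859.
- Diet, d = 0.11: 4 × (3.339/0.11)² × 0.75 × 1.205 ≈ 3,331.

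| Design effect | Activity | Diet |
|---|---|---|
| 1.205 (percentages as shares of participants) | 859 | 3,331 |
| 1.243 (mean household size 1.81) | 888 | 3,438 |
| 1.248 (4,200 users in 2,300 households) | 890 | 3,450 |
| 1.298 (percentages as shares of households) | 925 | 3,588 |

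Other ways of forming the design effect at ICC 0.3 widen the ranges to 824–954 and 3,194–3,692.

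**4. Position at the switch.** The threshold is 0.8 × 4,200 = 3,360. Each stated MDES is multiplied by √(4,200/3,360) = 1.118.

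| Outcome | MDES at 3,360 | Target |
|---|---|---|
| MVPA (min/day) | 2.68 | 5.2 |
| Steps/day | 415 | 819 |
| Fruit and vegetables (g/day) | 20.9 | 21 |
| Fibre (g/day) | 0.827 | 0.83 |
| Free sugars (% food energy) | 0.704 | 0.69 |
| Saturated fat (% food energy) | 0.347 | 0.35 |

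Power for 0.11 SD at 3,360 is 80.4% (DE 1.205) or 78.9% (DE 1.243), and 75.4–82.3% over all ICC 0.3 variants. With DE 1.205, power for the 0.2 SD activity target is above 99% at 3,360 and at 2,000, and about 82% at 900.

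**The case against.** **On the footnotes.** The main text of Table 2 points the right way, since it speaks of attrition judged too high, and it asks only that payment be considered. The rows are also marked as triggered at M5 and at M3 and M5, which suggests that the decision may already have been taken on a sensible reading. A reader might infer that good retention would start the payments, or that they were made on the wrong basis. The documents support neither inference. What remains is that the only numerical definition is reversed, and it appears twice.

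**On the switch.** A reader might infer that the 5-month endpoint is dropped while the sample still meets the plan's targets. For the four diet outcomes this is not so. The rule acts only below 3,360, almost exactly where 80% power for 0.11 SD is lost, and free sugars is already slightly short of its target there. Nor is 5 months dropped, because footnote 15 keeps those results in the report. Table 2 also refers to Table 7 rather than to the Table 5 targets; on that benchmark an 80% tolerance raises every MDES by about 12%, which is an understandable margin.

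A reader might go further and set thresholds at the computed sample sizes. That does not follow either. For activity, 925 of 15,500 randomised is about 6% retention, where selection and differential attrition matter more than power. For diet, 3,588 lies above 3,360 and would leave 5 months sooner. One cautious rule for both families is defensible. It still sits poorly with section 2.6.3.7 for activity, and Table 2 does not say whose n it counts, although section 2.6.3.1 expects activity attrition to be lower and tests it separately.

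**Conclusion.** Footnotes 13 and 14 are wrong as written and need correction. Against about 3,600 expected non-providers, the trigger is met at about 3,240 or fewer and cannot be met when attrition exceeds plan. This rests only on the wording and on the rounded totals in Table 6. The practical effect is limited because payment is discretionary.

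The switch is a lesser matter of clarity and fit. The 3,360 threshold suits diet (about 3,330 to 3,450 users needed under the best-fitting design effects). It is stricter than power requires for activity (about 860 to 925 users), where the conclusion could move to 3 months with power above 99% remaining just below the threshold. Power alone does not settle where an activity threshold should lie. These figures assume an overall two-sided alpha of 0.05, ICC 0.3, baseline correlation 0.5, and an even pooled-versus-control split kept at the reduced sample size.

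**What to change.** 1. Reverse the direction in footnotes 13 and 14 and choose one count. Either the number of users providing data is at least 10% smaller than expected (about 10,710 or fewer at 1 month), or the number not providing data is at least 10% larger than expected (about 11,540 or fewer providing). If the payments have already been decided, record which reading was used.
2. In the last row of Table 2, state whose n is counted at 5 months. Consider applying the switch separately to activity and diet.
3. Reconcile that row with section 2.6.3.7, so that one condition governs the switch. Do not set it on power alone; let the level of attrition and its difference between arms bear on it too.

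The first item costs two sentences. The others need a short decision and a wording change. None needs new data, or budget beyond the payments already foreseen.

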2.2.4 Randomisation

Randomisation will be conducted at the household level. This approach has two advantages over individual-level randomisation: (i) avoids the risk of contamination within the same household (but opens up the possibility of additive effects of multiple household members being in treatment together); (ii) reduces the risk that we alienate and / or confuse users in the control group whenever they cohabit with someone assigned to a treatment arm.

Users will enter randomisation only if/when they have completed the baseline phase. This implies that the day of randomisation is different across users even within the same households: it always happens at the end of their baseline phase (if successful), but the exact calendar day depends on when they have downloaded the app, when they have completed the onboarding, and how long it took them to complete the baseline phase (see Figure 1 for an example from a user's perspective).

The randomisation algorithm developed by HUL would then:

1. Check if another user from the same household has already been randomised

¹⁴ We consider the attrition too high if the number of users not providing their data is 10% smaller than expected at the start of the 1 month mark (see Table 6 for the expected attrition at different trial stages).

¹⁵ Results for the 5m mark will still be reported; however, we will rely on results from the 3m mark to provide an assessment of the impact of offering financial incentives.

based on their full addresses (including postcode).

- 2. If YES, the algorithm assigns this user to the same trial arm
- 3. If NO, the algorithm generates a random number from 1-100 (inclusive) for the user.
- 4. Based on the rule described in Figure 2, users are assigned to one of the 4 trial arms. Note that the control arm will be larger than the other arms. This is because at the analysis stage (5m mark), we aim at having 3 users in the control group for each user in the treatment arms. However, we expect attrition to differ across control and treatment groups, as shown in Table 6 in Section 2.4.2.4.. Based on these attrition estimates, at randomisation 12% of users will be assigned to the high incentive arm, 12% to the medium incentive arm, 15% to the low incentive arm, 61% to the control arm.

BIT's in-house IT expert will quality assure the code of the randomisation algorithm developed by HUL before the trial launch.

Figure 1. Onboarding and baseline phase from a user's point of view¹⁶.

User A downloads the app on trial launch date, their onboarding phase lasts 2 days and their baseline phase lasts 10 days (as they provide the required data within 10 days), hence they enter randomisation on day 12 after trial launch day. **User B** downloads the app three days on day 3 after the trial launch day, their onboarding phase lasts 1 day and their baseline phase lasts 12 days (as they provide the required data within 12 days), hence they enter randomisation on day 15 after trial launch day. **User C** downloads the app on day 4, their onboarding phase lasts 3 days and their baseline phase lasts 14 days (as in 2 weeks they provide 1 dietary recall instead of 2 and at least 5 days of PA), hence they enter randomisation on day 20. **User D** downloads the app on day 5, their onboarding phase lasts for 1 day and their baseline phase lasts14 days, at the end of which they have not provided the required data, hence they cannot enter randomisation and their user journey ends.

¹⁶ In Figure 1, the recruitment period lasts for 4 weeks, which is the best-case scenario. This may be extended to 8 weeks if needed to achieve the target sample size.

[figure not shown]

Figure 2. Randomisation process

2.3 Outcomes

We propose three types of outcomes for our impact evaluation: primary, and exploratory (see Table 3).

The primary outcomes consist of **2 physical activity outcomes** and **4 dietary outcomes**.

- The primary physical activity outcomes include: (i) moderate and vigorous physical activity (MVPA) in minutes per day and (ii) daily steps measured objectively through a wearable device.
- The primary dietary outcomes include (i) fruit and vegetables (g/day) and (ii) fibre (g/day), (iii) saturated fat (% of energy from food), and (iv) free sugars (% of energy from food) measured through two Intake24 questionnaires per measurement time point.

The secondary outcomes include (i) daily energy expenditure as measured by the wearable, (ii) daily energy intake as measured by 24-hour dietary recalls (Intake24 surveys), (iii) a healthy eating score based on consumption of key food groups, macro- and micronutrients, and (iv) self-reported weight.

The exploratory outcomes include unintended health impact of the interventions, such as (i) sleep quality and (ii) mental well-being. It will also include motivation to change (iii) PA and (iv) diet.

Outcomes	Category	Metric	Collection method	Data collection point	Analysed
Primary	Primary PA MVPA (min/day) Daily steps		Wearable device	Throughout the full duration of the pilot	Effect at 1m, 3m, 5m marks
	Diet	 Fruit and vegetables (g/day) Fibre (g/day) Free sugars (% daily food energy) Saturated Fat (% daily food energy) 	24h recall survey (Intake24)	Baseline, 1m, 3m, 5m marks	Effect at 1m, 3m, 5m marks
Secondary	PA	 Energy expenditure (kcal/day) 	Wearable device	Throughout the full duration of the pilot	Effect at 5m mark
	Diet	 Energy intake (kcal/day) 	24h recall survey (Intake24)	Baseline, 1m, 3m, 5m marks	Effect at 5m mark

Table 3. Outcome measures

		 A healthy eating score based on consumption of key food groups, macro- and micronutrients, (see Section 2.3.1.2 for details) 			
	Weight	Weight (kg)	Self-reported survey	Baseline, 1m, 3m, 5m marks	Effect at 5m mark
Exploratory	Motivation to change	Motivation to change diet	In-App survey	Baseline, 5m marks	Effect at 5m mark
		Motivation to change PA	In-App survey	Baseline, 5m marks	Effect at 5m mark
Unintendec impact on mental and physical		Self-reported mental well-being measured by WHO-5 Index (0~100, 0 = worst, 100 =best)	In-App survey	Baseline, 1m, 3m, 5m marks	Effect at 5m mark
	well-being	Sleep quality (hours/day)	Wearable device	Throughout the full duration of the pilot	Effect at 5m mark

2.3.1 Primary outcomes

We propose two categories of primary outcomes for our impact evaluation outcomes that relate to PA and outcomes that relate to diet. The overarching rationale for selecting these outcomes is focusing on behaviours that are directly encouraged by the in-app challenges - please see HUL's intervention design plan and the complementary Theory of Change note for further detail.

2.3.1.1 Primary outcome - physical activity

The proposed primary outcomes for PA include: (i) moderate and vigorous physical activity (MVPA) in minutes per day and (ii) daily steps. We chose those two outcomes chiefly because they have shown to provide clinical health benefits.

MVPA. We focus on daily MVPA minutes as one of the PA primary outcomes because cumulative MVPA mins have shown to provide various clinical health benefits (e.g. reducing BMI, cholesterol level, and blood pressure)¹⁷. Additionally, a meta-analysis of interventions to reduce sedentary time showed that both light-intensity physical activity (e.g. walking) and MVPA increased energy expenditure

¹⁷ Hajna, S., Ross, N. A., & Dasgupta, K. (2018). Steps, moderate-to-vigorous physical activity, and cardiometabolic profiles. *Preventive Medicine*, *107*, 69–74. doi: 10.1016/j.ypmed.2017.11.007

in adults but interventions increasing MVPA had a larger effect on energy expenditure than those focused on light-intensity activities ¹⁸. Currently, the CMO's Physical Activity Guidelines recommends at least 150 minutes of MVPA per week for adults for good health.

Steps. We include daily steps as another primary outcome for three reasons. First, daily steps, like MVPA, have been widely used in previous similar studies and including it would increase the comparability of our results. Second, daily steps have also shown health benefits: a recent study¹⁹ has found that a greater number of steps per day was significantly associated with lower all-cause mortality among U.S. adults. Third, daily steps are a good proxy for the degree to which one has led a sedentary lifestyle, a risk that has been highlighted by the CMO's Physical Activity Guidelines.

These two outcomes are also directly incentivised by the app. Some incentives will be tied to a 'Let's get moving' (Do ((minutes goal)) minutes ((days goal)) times each week) or 'Step it up' challenge ((Do at least (goal steps) per day) (see the *Theory of Change* note for details), making these two outcomes good candidates to measure the direct effects of the financial interventions.

The physical activity data is passively collected. All devices, including the device provided by HUL, can detect PA metrics (heart rates, step counts, MVPA, calories and sleep) automatically without the user's input. However, for HUL to capture this data, the device needs to be synced with the app on a regular basis.

Daily steps are directly measured by the wearable. MVPA is calculated as the sum of vigorous and moderate activities. All devices define a PA to be "vigorous" if the user's heart rate falls within the cardio or peak heart rate zones. Most of the devices auto-classify a "moderate" PA if two conditions are met: (1) the heart rate is within fat-burning heart rate zones; (2) sufficient movements detected by accelerometers built in the wearables.

2.3.1.2 Primary outcome - diet

As dietary change evokes a spectrum of changes, the study will use four primary outcomes for diet.²⁰

¹⁸ Biswas A, Oh PI, Faulkner GE, Bonsignore A, Pakosh MT, Alter DA. The energy expenditure benefits of reallocating sedentary time with physical activity: a systematic review and meta-analysis. Journal of Public Health. 2018 Jun 1;40(2):295-303.

¹⁹ Saint-Maurice, P. F., Troiano, R. P., Bassett, D. R., Graubard, B. I., Carlson, S. A., Shiroma, E. J., ... Matthews, C. E. (2020). Association of Daily Step Count and Step Intensity With Mortality Among US Adults. *JAMA*, *323*(12), 1151–1160. doi: 10.1001/JAMA.2020.1382

²⁰ In previous versions of the evaluation protocol, calorie intake had been selected as the primary outcome for diet. The DOPA/OHID expressed concerns around use of kcal as the primary outcome measure for diet, in particular around i) underreporting, and ii) the fact that the pilot is not a weight loss programme and so there was the concern of not being able to detect a change in kcals even if the pilot did improve participants' diet. Following further conversations with the DOPA/OHID, BIT and DHSC agreed on the list of primary outcomes included in the current evaluation protocol, that reflect behaviours that are directly incentivised by the programme.

These include:

- Fruit and vegetables (g/day)
- Fibre (g/day)
- Saturated fat (% daily food energy²¹ intake)
- Free sugars (% daily food energy intake)

Evidence suggests that people typically consume insufficient amounts of fruit and vegetables and fibre whilst overconsuming saturated fat and free sugars.²² (Also see Appendix C for an overview of the recommended dietary intake **according to UK** dietary recommendations).

Tackling the primary outcomes above, might benefit health:

- Fruit and vegetable consumption: The health benefits of increased fruit and vegetable consumption include reduced risk of cardiovascular disease, cancer, and all-cause mortality.^{23 24} A recent meta-analysis also provided moderate certainty evidence that consuming fresh fruit promotes weight maintenance or modest weight loss over periods of 3–24 weeks.²⁵ This is in line with other evidence suggesting increased fruit and vegetable consumption can support maintenance of a healthy weight.^{26 27}
- **Fibre consumption:** Consumption of whole-grain and dietary fibre has been associated with lower mortality, and lower risk of CVD, obesity, and diabetes.²⁸
